### PK Evaluation

Once the subject is on a stable dose of Xyrem, PK Nights 1 and 2 can be scheduled for a protocol-specified clinic visit or for an additional clinic visit.

- If not done at a previous visit:
  - Obtain additional documented assent and consent for the PK evaluation.
  - Review the inclusion/exclusion criteria for subjects participating in the PK evaluation.
  - Obtain blood samples for coagulation (PT/INR and PTT) within 30 days of PK Night 1
- Follow procedures for PK Nights 1 and 2 in [Section 7.1.3](#).

Xyrem® (sodium oxybate) oral solution  
Clinical Study Protocol: 13-005 Amendment 5

Jazz Pharmaceuticals.

#### 7.4.2 Phone Call Visits 6, 8, 10, 11, 13, 14 (Weeks 16, 22, 30, 34, 43, and 48 from Day 1)

- Record all AEs on the AE CRF.
- Record all concomitant medications on the concomitant medications CRF.
- Administer the following:
  - C-SSRS ([Appendix 8](#)) (Since Last Visit version for subjects  $\geq 12$  years of age and Children's Since Last Visit version for subjects  $< 12$  years of age)
  - CDI 2:SR[S] ([Appendix 9](#))
  - MASC-10 ([Appendix 10](#))

#### 7.4.3 Visit 15 Week 52 or Part 1 Early Termination

If the subject will be continuing directly into Part 2, the Open-Label Continuation Period, see [Section 7.5](#).

- Perform a physical examination, including a brief neurological examination and a Tanner Stage Assessment ([Appendix 5](#)) but excluding a full genitourinary exam.
- Record height and weight in ordinary indoor clothes (without shoes).
- Review Cataplexy Frequency Diary.
- Review Study Drug Dosing Diary.
- Administer the following:
  - ESS (CHAD) ([Appendix 6](#))
  - SF-10 ([Appendix 7](#))
  - C-SSRS ([Appendix 8](#)) (Since Last Visit version for subjects  $\geq 12$  years of age and Children's Since Last Visit version for subjects  $< 12$  years of age)
  - CDI 2:SR[S] ([Appendix 9](#))
  - MASC-10 ([Appendix 10](#))
- Obtain vital signs (systolic and diastolic blood pressure, pulse/heart and respiratory rate, and body temperature) after the subject has been resting supine for at least 5 minutes.
- Obtain urine samples for urinalysis.
- Perform alcohol test and urine drug screens.
- Obtain urine sample for pregnancy test (only perform for female subjects who have reached menarche).
- Obtain a 12-lead ECG.
- Record all AEs on the AE CRF.
- Record all concomitant medications on the concomitant medications CRF.
- Collect study drug dispensed at the previous visit and measure compliance.
- Perform End of Study (Part 1) PSG according to the procedures for all subjects in Column 4 of [Table 6](#). If the subject withdraws early from the study during the Open-Label Safety Period, perform the PSG if subject is willing to be dosed with study drug

on this PSG night. Part 1 early termination PSG does not apply for subjects who discontinue before entering the Open-Label Safety Period.

- Obtain blood samples for the following the morning after the PSG night:
  - Fasting blood sample for GH, IGF-1, and prolactin
  - Routine hematology and chemistry
  - For girls <8 years of age: estradiol, FSH, and LH
  - For boys <9 years of age: testosterone, FSH, and LH
- If the subject will not be continuing into Part 2, record the reason why and schedule the Safety Follow-up visit.

#### 7.4.4 Visit 16 Safety Follow-up Visit

The Safety Follow-up Visit must be completed 14 days (+3 days) after the last dose of study drug for subjects who complete Part 1 of the study and are not continuing directly into Part 2 or for subjects who terminate early from Part 1.

- Record height and weight in ordinary indoor clothes (without shoes).
- Obtain vital signs (systolic and diastolic blood pressure, pulse/heart and respiratory rate, and body temperature) after the subject has been resting supine for at least 5 minutes.
- Administer the following:
  - C-SSRS ([Appendix 8](#)) (Since Last Visit version for subjects  $\geq 12$  years of age and Children's Since Last Visit version for subjects <12 years of age)
  - CDI 2:SR[S] ([Appendix 9](#))
  - MASC-10 ([Appendix 10](#))
- Record all AEs on the AE CRF.

Subjects will not be given study drug during this 2-week follow-up period but are expected to be treated for their cataplexy and EDS with commercially available medications as appropriate during this time by their treating physicians.

### 7.5 Part 2 Open-Label Continuation Period for Subjects Continuing Directly into Part 2 after Completing Part 1

#### 7.5.1 Visit 15 for Subjects Continuing in Part 2 (Onsite)

- Confirm that subject provided assent and ICF signed by parent(s) or guardian(s) for Protocol Amendment 5.
- Perform a physical examination, including a brief neurological examination and a Tanner Stage Assessment ([Appendix 5](#)) but excluding a full genitourinary exam.
- Record height and weight in ordinary indoor clothes (without shoes).
- Review Cataplexy Frequency Diary.
- Review Study Drug Dosing Diary.
- Administer the following:
  - ESS (CHAD) ([Appendix 6](#))

Xyrem® (sodium oxybate) oral solution  
Clinical Study Protocol: 13-005 Amendment 5

Jazz Pharmaceuticals.

- 
- SF-10 ([Appendix 7](#))
  - C-SSRS ([Appendix 8](#)) (Since Last Visit version for subjects  $\geq 12$  years of age and Children's Since Last Visit version for subjects  $< 12$  years of age)
  - CDI 2:SR[S] ([Appendix 9](#))
  - MASC-10 ([Appendix 10](#))
  - Obtain vital signs (systolic and diastolic blood pressure, pulse/heart and respiratory rate, and body temperature) after the subject has been resting supine for at least 5 minutes.
  - Obtain urine samples for urinalysis.
  - Perform alcohol test and urine drug screens.
  - Obtain urine sample for pregnancy test (only perform for female subjects who have reached menarche).
  - Obtain a 12-lead ECG.
  - Record all AEs on the AE CRF.
  - Record all concomitant medications on the concomitant medications CRF.
  - Collect study drug dispensed at the previous visit and measure compliance.
  - Perform End of Study (Part 1) PSG according to the procedures for all subjects in Column 4 of [Table 6](#).
  - Obtain blood samples for the following the morning after the PSG night:
    - Fasting blood sample for GH, IGF-1, and prolactin
    - Routine hematology and chemistry
    - For girls  $< 8$  years of age: estradiol, FSH, and LH
    - For boys  $< 9$  years of age: testosterone, FSH, and LH
  - Dispense study drug. (Access Interactive Response Technology [IRT].) Provide instructions for dose administration and, if flavored diluent is requested and available, the preparation of study drug with flavored diluent to subjects/parent(s)/guardian(s). See [Section 6.10](#).
  - Determine when the subject will be 18 years of age. Schedule the Part 2 Study Termination Visit to occur **prior to** the subject's 18th birthday.

#### 7.5.2 Visits 19, 20, 22, 23, 25, 26, 28, 29, 31, 32, 34, 35, 37, 38, 40, and 41 (Phone Call)

- Record all AEs on the AE CRF.
- Record all concomitant medications on the concomitant medications CRF.
- Determine when the subject will be 18 years of age. Schedule the Part 2 Study Termination Visit to occur **prior to** the subject's 18th birthday.

#### 7.5.3 Visits 21, 27, 33, and 39 (Onsite)

- Record height and weight in ordinary indoor clothes (without shoes).

Xyrem® (sodium oxybate) oral solution  
Clinical Study Protocol: 13-005 Amendment 5

Jazz Pharmaceuticals.

- 
- Obtain vital signs (systolic and diastolic blood pressure, pulse/heart and respiratory rate, and body temperature) after the subject has been resting for at least 5 minutes.
  - Record all AEs on the AE CRF.
  - Record all concomitant medications on the concomitant medications CRF.
  - Collect study drug dispensed at the previous visit and measure compliance.
  - Dispense study drug. (Access IRT.) Provide instructions for dose administration and, if flavored diluent is requested and available, the preparation of study drug with flavored diluent to subjects/parent(s)/guardian(s). See [Section 6.10](#).
  - Determine when the subject will be 18 years of age. Schedule the Part 2 Study Termination Visit to occur *prior to* the subject's 18th birthday.

#### 7.5.4 Visits 24, 30, and 36 (Onsite)

- Record height and weight in ordinary indoor clothes (without shoes).
- Perform alcohol test and urine drug screens.
- Obtain urine sample for pregnancy test (only perform for female subjects who have reached menarche).
- Obtain vital signs (systolic and diastolic blood pressure, pulse/heart and respiratory rate, and body temperature) after the subject has been resting for at least 5 minutes.
- Record all AEs on the AE CRF.
- Record all concomitant medications on the concomitant medications CRF.
- Collect study drug dispensed at the previous visit and measure compliance.
- Dispense study drug. (Access IRT.) Provide instructions for dose administration and, if flavored diluent is requested and available, the preparation of study drug with flavored diluent to subjects/parent(s)/guardian(s). See [Section 6.10](#).
- Determine when the subject will be 18 years of age. Schedule the Part 2 Study Termination Visit to occur *prior to* the subject's 18th birthday.

#### 7.5.5 Part 2 Study Termination/Part 2 Early Termination Visit 42 (Onsite)

- Record height and weight in ordinary indoor clothes (without shoes).
- Perform alcohol test and urine drug screens.
- Obtain urine sample for pregnancy test (only perform for female subjects who have reached menarche).
- Obtain vital signs (systolic and diastolic blood pressure, pulse/heart and respiratory rate, and body temperature) after the subject has been resting for at least 5 minutes.
- Record all AEs on the AE CRF.
- Record all concomitant medications on the concomitant medications CRF.
- Collect study drug dispensed at the previous visit and measure compliance.

## 7.6 Part 2 Open-Label Continuation Period for Subjects Re-enrolling after Completing Part 1

After the subject has provided assent and a parent(s) or guardian(s) has signed an ICF in accordance with local IRB/IEC requirements, the subject may be screened for re-enrollment in Part 2. All subjects will provide their written informed consent prior to the performance of any study-related procedures. The Part 2 Screening Visit (Visit 17) starts when a subject is registered for Part 2 in IRT. Screening will occur within 2 weeks before dosing. If needed, additional screening time may be granted with permission of the Medical Monitor.

### 7.6.1 Part 2 Screening Visit 17 (Onsite) for Subjects Re-enrolling after Completing Part 1 of the Study

- Obtain subject assent and ICF signed by parent(s) or guardian(s).
- Update the parent or guardian's contact information
- Review the inclusion/exclusion criteria for Part 2.
- Interview parent(s)/guardian(s) to determine if the home situation is safe for Xyrem use and storage, and assess if there is a risk of use or abuse by family members or others living in the home.
- Review the subject's previously recorded medical history and update any new medical history information. Record any new medical history that occurs after Visit 16 and prior to re-enrollment. (Any new clinically significant condition with onset after the last Part 1 visit (Visit 16) until assent/consent is provided in Part 2 should be recorded as medical history.)
- Record all prior medications, including OTC and health and dietary supplements taken during the 2 weeks before Screening. Also record any concomitant medications.
- Confirm the subject's current Xyrem usage. If the subject is currently on Xyrem, record the subject's prescribed usual dose and regimen of Xyrem. If currently on Xyrem, the subject should be on a stable dose. If the subject has been off Xyrem, record if the subject has been off Xyrem for  $\geq 1$  month.
- Perform a physical examination, including a brief neurological examination.
- Record height and weight in ordinary indoor clothes (without shoes).
- Obtain blood samples for the following: \*
  - Routine hematology and chemistry (see [Table 2](#))
  - Serum pregnancy test (only for female subjects who have reached menarche)
- Obtain urine samples for urinalysis.\*
- Perform alcohol test and urine drug screens.\*
- Obtain vital signs (systolic and diastolic blood pressure, pulse/heart and respiratory rate, and body temperature) after the subject has been resting for at least 5 minutes.

\* Subjects who re-enroll within 2 weeks of Visit 15 do not need clinical labs, drug screen, alcohol test, or serum pregnancy test at the Part 2 Screening.

## 7.6.2 Part 2 Visits for Subjects Re-enrolling Who Do Not Require Titration

Subjects who re-enroll after completing Part 1 do not require titration if they have continued to take Xyrem and are on a stable dose.

### 7.6.2.1 Visit 18 (Onsite) Subjects Re-enrolling Who Do Not Require Titration

- Review the inclusion/exclusion criteria for Part 2 to determine the subject's eligibility to continue participating in the study.
- Record height and weight in ordinary indoor clothes (without shoes).
- Perform alcohol test and urine drug screens.
- Obtain urine sample for pregnancy test (only perform for female subjects who have reached menarche).
- Obtain vital signs (systolic and diastolic blood pressure, pulse/heart and respiratory rate, and body temperature) after the subject has been resting for at least 5 minutes.
- Record all AEs that occur after assent was given and the ICF was signed on the AE CRF.
- Record all concomitant medications that were taken after assent was given and the ICF was signed on the concomitant medications CRF.
- Dispense study drug. (Access IRT.) Provide instructions for dose administration and, if flavored diluent is requested and available, the preparation of study drug with flavored diluent to subjects/parent(s)/guardian(s). See [Section 6.10](#).
- Determine when the subject will be 18 years of age. Schedule the Part 2 Study Termination Visit to occur **prior to** the subject's 18th birthday.

### 7.6.2.2 Visits 19 through 42 for Subjects Who Do Not Require Titration

Follow the activities in [Sections 7.5.2](#) through [7.5.5](#).

## 7.6.3 Part 2 Visits for Subjects Re-enrolling Who Require Titration

### 7.6.3.1 Visit 18 (Onsite) Subjects Re-enrolling Who Require Titration – Begin Titration (Week T1)

Titration is required for subjects who are re-enrolling after completing Part 1 of the study and have been off Xyrem for  $\geq 1$  month. For subjects who have been off Xyrem for less than 1 month, titration may also be required per the Investigator's judgment. Subjects will be titrated to Xyrem as described in [Section 3.1.2](#). The Part 2 Titration may last up to 10 weeks. Once it is determined that the subject has achieved clinical benefit in cataplexy and EDS while maintaining tolerability, the subject may remain on that stable dose through the remainder of the titration period. However, Xyrem dose adjustment due to tolerability and efficacy is permitted per the Investigator's judgment.

Follow the activities in [Section 7.6.2.1](#).

Xyrem® (sodium oxybate) oral solution  
Clinical Study Protocol: 13-005 Amendment 5

Jazz Pharmaceuticals.

#### 7.6.3.2 Visits 18.1, 18.2, 19, 19.1, 20, 20.1 (Phone Calls) Subjects Re-enrolling Who Require Titration

Study activities for Titration Phone Visits 18.1 (Week T2 +3 days), 18.2 (Week T3 +3 days), 19 (Week T4 +3 days), 19.1 (Week T7 +3 days), 20 (Week T8 +3 days), 20.1 (Week T10 +3 days) are as follows:

- Record all AEs that occur after assent was given and the ICF was signed on the AE CRF.
- Record all concomitant medications that were taken after assent was given and the ICF was signed on the concomitant medications CRF.
- Determine if additional dose titration is necessary.
- Determine when the subject will be 18 years of age. Schedule the Part 2 Study Termination Visit to occur *prior to* the subject's 18th birthday.

#### 7.6.3.3 Visits 21 through 42 for Subjects Who Require Titration

Follow activities in [Sections 7.5.2](#) through [7.5.5](#).

## 8 QUALITY CONTROL AND ASSURANCE

The study will be conducted according to GCP guidelines and according to local and national law. Quality audits may be performed at the discretion of Jazz Pharmaceuticals or its designee.

## 9 PLANNED STATISTICAL METHODS

### 9.1 General Considerations

The primary objectives of this study are to evaluate the efficacy and safety of Xyrem in the treatment of cataplexy in narcolepsy in pediatric subjects. Secondary objectives are to evaluate the efficacy of Xyrem in the treatment of EDS in pediatric subjects with narcolepsy with cataplexy, to characterize the PK of Xyrem given as two doses to children and adolescents (ages 7-17 years) with narcolepsy with cataplexy, and to evaluate the safety of titrating Xyrem in children and adolescents to an effective and tolerable dose.

Non-categorical efficacy parameters will be analyzed by non-parametric analysis of covariance (ANCOVA). Ordinal categorical parameters, including CGIc and PGIC, will be analyzed using Cochran–Mantel–Haenszel (CMH) tests for row mean score difference. PK parameters will be assessed by analysis of variance (ANOVA) models using natural log-transformed data. Safety data will be summarized using descriptive statistics. When data are reported by age group, either ages 7-11 years or ages 12-17 years, subjects will be summarized by age at Visit 2 (start of the Stable-Dose Period) for subjects on Xyrem at study entry and at Visit 1.1 (start of the Titration Period) for Xyrem-naïve subjects.

Xyrem® (sodium oxybate) oral solution  
Clinical Study Protocol: 13-005 Amendment 5

Jazz Pharmaceuticals.

---

## 9.2 Determination of Sample Size

The study will enroll pediatric subjects who are diagnosed with narcolepsy with cataplexy and who are between 7 and 16 years of age, inclusive, to ensure subjects are <18 years of age at the end of Part 1 of the study. At least 100 subjects will be enrolled in the study to assess the safety of Xyrem in this pediatric population.

Prior to Amendment 4, a sample size of 70 subjects was planned to enter the randomized-withdrawal (Double-Blind Treatment) period. This sample size was estimated based on repeated resampling of the data with replacement (bootstrapping) from previous narcolepsy trials in adults (GHB-2 and OMC-SXB-15). The analysis showed that a sample of 35 subjects on Xyrem (sodium oxybate) treatment had at least 40% difference from endpoint to baseline in the mean weekly number of cataplexy attacks, as a percentage of endpoint, over 95% of the time. The present study (13-005) differs from Studies GHB-2 and OMC-SXB-15 in that pediatric subjects will be enrolled instead of adults, the study design is randomized-withdrawal versus a standard randomized treatment study, and the length of the randomized period is 2 weeks for 13-005 versus 4 weeks for GHB-2 and 8 weeks for OMC-SXB-15. Discounting for these factors, a sample of 35 subjects in each arm was expected to have at least 80% power to detect a difference between the two treatment groups of 40% in the percentage change in the mean weekly number of cataplexy attacks during the 2-week Double-Blind Treatment Period of the study as compared with the mean weekly number of cataplexy attacks during the last 2 weeks of the immediately preceding stable-dose period, using a two-sided alpha of 0.05.

Every effort will be made to enroll approximately 30 subjects on Xyrem at study entry of the anticipated 100 subjects enrolled. Other subjects enrolled will be Xyrem naïve at study entry.

A subset of the subjects who are taking Xyrem at a stable dose for their narcolepsy symptoms will participate in the PK evaluation. Up to 18 subjects in each of the two age groups (7-11 year olds and 12-17 year olds) will be enrolled to ensure a minimum of 12 completers in each age group. If the variability of PK data in children and adolescents is comparable to that of adults, a sample size of 12 completers in each age group is expected to provide adequate precision to characterize the PK of sodium oxybate in each age group. However, when sufficient data are obtained to characterize the PK profile with adequate precision during the study, as determined by the Data and Safety Monitoring Board (DSMB), or when enrollment of 100 subjects in the study has been reached, enrollment for the PK evaluation will stop and available data will be used for analysis.

## 9.3 Analysis Populations

The Safety Population will consist of all subjects who are dispensed study drug. This population will be used for tables and listings of safety data. This population will also be used to summarize efficacy data as appropriate. The Safety Population will be additionally categorized by period and by whether the subject took study drug during the different study periods.

Xyrem® (sodium oxybate) oral solution  
Clinical Study Protocol: 13-005 Amendment 5

Jazz Pharmaceuticals.

The PK Half-Dose Population will consist of all subjects who have any PK data for PK Night 1 when subjects receive one half of their usual stable dose. This population will be used for listings and descriptive statistics of the half-dose PK data.

The PK Full-Dose Population will consist of all subjects who have any PK data for PK Night 2 when subjects receive their usual stable dose. This population will be used for listings and descriptive statistics of the full-dose PK data.

The PK Completer Population will consist of all subjects who have PK data for both PK nights. This population will be used for evaluating within subject dose proportionality.

The Efficacy Population will consist of all subjects who are randomized to Xyrem or Xyrem placebo and who complete at least 5 days of dosing in the Double-Blind Treatment Period. This population will be used as the main analysis population for tables of the primary and secondary efficacy endpoints.

The Randomized Population will consist of all subjects who are randomized to Xyrem or Xyrem placebo for the Double-Blind Treatment Period of the study. This population will be used to summarize exposure to double-blind treatment. This population may also be used for summaries of safety data specific to the Double-Blind Treatment Period. This population may also be used for an additional analysis of the primary and/or secondary efficacy endpoints.

The Continued Access Population will consist of all subjects who took study drug in Part 2. This population will be used for tables and listings of Part 2 data.

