## 6.10 Dispensing Study Drug

Subjects on Xyrem at study entry will continue dosing with their own supply of drug during the Part 1 Screening Period; however, appropriate study drug will be provided on the screening PSG night and will be administered by or under the supervision of qualified study site personnel. Study drug will be dispensed to Xyrem-naïve subjects at the beginning of the Part 1 Open-Label Titration Period (Visit 1.1) and to subjects on Xyrem at study entry at the start of the Stable-Dose Period (Visit 2). For subject who re-enroll in Part 2, study drug will be dispensed at Visit 18. Study drug will be dispensed at study visits, excluding phone visits, according to the schedules of events ([Appendix 1](#), [Appendix 2](#), [Appendix 22](#), [Appendix 23](#), and [Appendix 24](#)).

Study drug doses should be prepared with the dosing dispenser (syringe) that is supplied in the study drug kit (dosing instructions provided by Jazz Pharmaceuticals). Instructions for dose administration of the study drug will be provided to subjects/parent(s)/guardian(s) by the site personnel.

Flavorant will be provided if available for study drug preparation if flavored diluent is requested by the subject and deemed appropriate by the Investigator (excluding PSG and PK nights). Instructions for preparation of study drug with flavored diluent will be supplied if flavored diluent is to be used. Additional drug dispensing visits will be made as required by State or local regulations.

On all PSG and PK nights, study drug will be administered by or under the supervision of qualified study site personnel.

The Investigator or designated pharmacist will maintain accurate records for all study drug administered or dispensed.

Xyrem® (sodium oxybate) oral solution  
Clinical Study Protocol: 13-005 Amendment 5

Jazz Pharmaceuticals

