  - The Investigator must thoroughly review results of all screening procedures and confirm all eligibility criteria prior to enrolling the subject in the study. The PSG must be completed and reviewed before the subject is enrolled (For the PSG, follow the procedures in Column 2 of [Table 6](#) for “Subjects on Xyrem at study entry.”)
  - Schedule next visit
- 7.1.2 Start of Stable-Dose Period, Subjects on Xyrem at Study Entry (Visit 2, Day 1)
- Review inclusion/exclusion criteria to determine the subject’s eligibility to continue participating in the study.
  - Record height and weight in ordinary indoor clothes (without shoes).
  - Obtain vital signs (systolic and diastolic blood pressure, pulse/heart and respiratory rate, and body temperature) after the subject has been resting for at least 5 minutes.
  - Perform alcohol test and urine drug screens.
  - Obtain urine sample for pregnancy test (only for female subjects who have reached menarche).
  - Complete the CGIs for narcolepsy overall (current condition) ([Appendix 17](#)) and for cataplexy severity (current condition) ([Appendix 18](#)).

- Administer the following:
  - ESS (CHAD) ([Appendix 6](#))
  - SF-10 ([Appendix 7](#))
  - C-SSRS ([Appendix 8](#); Since Last Visit version for subjects  $\geq 12$  years of age and Children's Since Last Visit version for subjects  $< 12$  years of age)
  - CDI 2:SR[S] ([Appendix 9](#))
  - MASC-10 ([Appendix 10](#))
- Instruct subject and parent(s)/guardian(s) on how to complete the School Attendance Diary ([Appendix 14](#)) if the subject is currently attending school.
- Instruct subjects or parent(s)/guardian(s) on how to complete the Cataplexy Frequency Diary ([Appendix 11](#)).
- Review the dosing diaries for compliance with dosing (Study Drug Dosing Diary in [Appendix 12](#) and Stimulant Dosing Diary in [Appendix 13](#)).
- Record all AEs that occur after assent was given and the ICF was signed on the AE CRF.
- Record all concomitant medications that were taken after assent was given and the ICF was signed on the concomitant medications CRF.
- Dispense study drug at the subject's current stable dose. (Access IVRS/IWRS.) Provide instructions for dose administration and, if flavored diluent is requested and available, the preparation of study drug with flavored diluent to subjects/parent(s)/guardian(s). See [Section 6.10](#).

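### The Safety Population is defined by dispensing, so it leaves out children on Xyrem who take study drug on the screening PSG night and then fail screening

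*Protocol*

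**What the plan says.** Section 9.3 of the protocol sets the rule: "The Safety Population will consist of all subjects who are dispensed study drug". On its use it says: "This population will be used for tables and listings of safety data". It adds that the population will be "additionally categorized by period and by whether the subject took study drug during the different study periods". Later in the same section the Part 2 set is defined by drug taken: "The Continued Access Population will consist of all subjects who took study drug in Part 2".

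Section 6.10 covers how drug reaches children who enter on Xyrem. They use their own supply during screening, with one exception: "appropriate study drug will be provided on the screening PSG night and will be administered by or under the supervision of qualified study site personnel". Nothing is dispensed to them before Visit 2, the start of the Stable-Dose Period. Naïve children are first dispensed drug at Visit 1.1. The section's record-keeping sentence names administering and dispensing as alternatives.

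Table 6 has on-Xyrem children take their usual nightly dose at the screening PSG; naïve children are not dosed. AEs are recorded that night. Section 7.1.1 makes the PSG decisive for entry: "The PSG must be completed and reviewed before the subject is enrolled".

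**The concern.** A safety set normally contains everyone exposed to study drug under the protocol. Here, membership depends on an act (dispensing) that comes after the first exposure for one of the two entry groups, and a screening decision lies between the two. Children who are dosed and then screened out are therefore lost from the set.

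These are not random losses. One route out is exclusion 10, evidence of sleep-disordered breathing, assessed while the child is on drug. Section 9.9 lists respiratory depression among the events the DSMB monitors, and safety is Primary Objective 2. AEs are collected from assent or consent onward (Section 6.12.1), so the information exists. The definition gives it no place in the stated analysis set.

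**Working it through.** The protocol states no figure to reproduce. The check is a trace of subjects through the text, followed by a scale calculation under assumed rates.

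**Trace 1: on-Xyrem child who fails screening after the PSG**

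1. Consent and assent are given, and AE recording begins (Section 6.12.1).
2. On the screening PSG night the child takes site-supplied study drug at the usual nightly dose (Section 6.10; Table 6, column 2). AEs are recorded.
3. The PSG is reviewed and the child meets exclusion 10, or fails another criterion (Sections 4.3, 4.4 and 7.1.1).
4. The child is a screen failure and never reaches Visit 2, the first dispensing (Section 6.10).
5. Result: study drug taken, none dispensed, so the child is not in the Safety Population.

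The by-period, by-drug-taken categorization in Section 9.3 applies to the Safety Population. It partitions members and cannot add a non-member.

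**Trace 2: naïve child dispensed drug who takes none**

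1. No dose is given at the screening PSG (Table 6, column 1).
2. Drug is dispensed at Visit 1.1 and none is taken.
3. Result: in the Safety Population without exposure. Here the categorization does help, because the child can be identified and separated.

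This second case does not arise for on-Xyrem children at Visit 2, since they have already taken study drug at the PSG.

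**Scale**

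- Input from Sections 4.1 and 9.2: about 30 on-Xyrem subjects of an anticipated 100 enrolled, hence 100 − 30 = about 70 naïve.
- Assumed: f, the proportion of dosed on-Xyrem children who fail the screening PSG; and g, the proportion of naïve children who never take a dispensed dose. The protocol gives neither.

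If 30 are enrolled after a proportion f has failed, the number dosed is 30/(1 − f), and dosed failures are 30/(1 − f) − 30 = 30f/(1 − f).

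| f (assumed) | 30f/(1 − f) | Dosed children outside the set |
|---|---|---|
| 5% | 1.5/0.95 | 1.6 |
| 10% | 3/0.90 | 3.3 |
| 20% | 6/0.80 | 7.5 |

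Children dosed that night who fail screening for other reasons would add to these counts.

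For the never-dosed naïve children, 70g gives 0, 1.4 and 3.5 at g = 0%, 2% and 5%.

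**The case against.** The strongest reply is that little is lost. These children must have been on unchanged Xyrem doses for at least 2 months before screening (inclusion criterion 8). The study dose replaces their own supply for one night at the same dose. Serious events are reported within 24 hours whatever the analysis set, and the DSMB reviews safety data regularly. All of that stands. It limits the size of the gap and shows that oversight does not depend on it, but it does not put the children into the set.

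The sponsor might also say that dispensing was meant to include the PSG-night dose. Section 6.10 does not use the word that way; if that was the intention, one sentence would settle it.

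A reader might infer more than the protocol supports:

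- **That reported AE rates are biased downward.** This is not shown. A dosed screen failure brings one night of exposure and, for most event types, may add to the denominator without adding an event, which would lower incidence.
- **That the definition hides on-drug desaturations from the desaturation analysis.** Section 9.9 leaves the screening PSG out of that analysis for every subject, so changing the definition alone would not bring those findings in.
- **That every omitted child is a desaturation case.** Exclusion 10 can also be met through apnea-hypopnea limits, known apnea or hypoventilation, and screening can fail for unrelated reasons.
- **That never-dosed children sit in every denominator.** Section 9.3 allows them to be separated, and Section 9.9 also summarizes Part 1 AEs by dose.
- **That these children will appear in no listing at all.** A statistical analysis plan may add a screen-failure listing. What can be said is that the protocol's stated safety set excludes them.
- **That the Part 1 and Part 2 definitions contradict each other.** They serve different periods and need not match. The difference shows only that a drug-taken rule is already used in this protocol.

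**Conclusion.** The point holds in a limited form. On the protocol's wording, a child on Xyrem at entry who takes study drug on the screening PSG night and then fails screening is outside the population named for safety tables and listings, and nothing in Section 9.3 brings that child back. This follows from the text and rests on no assumed rate.

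The size is probably small: on-Xyrem screen failures only, one night each, about 2 to 8 children if 5% to 20% fail the PSG. That range is an assumption applied to a planned 30 enrolled. The direction of effect on overall AE rates is not established. Dispensed-but-never-dosed children are a minor matter. The change is still worth making, because a stated rule drops children dosed under the protocol whose data are already collected.

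**What to change.** In Section 9.3, define the Safety Population as all subjects who took at least one dose of study drug, including the dose given on the screening PSG night. Present dosed screen failures in a separate column or listing with their AEs and screening PSG result. The separate display is needed because the desaturation analysis in Section 9.9 omits the screening PSG, and because it keeps one-night exposures from being mixed with up to a year of treatment. The same wording also removes never-dosed children from the set.

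The cost is one sentence and one listing. AEs and PSG data from that night are already recorded, so no new collection is needed. Safety denominators change slightly.
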